1.1 STUDY SUMMARY

Objective

The primary objective of this study is to determine if patients with symptomatic vertebrobasilar stenosis or occlusion with compromised intracranial blood flow as demonstrated by magnetic resonance (MR) imaging are at increased risk for recurrent stroke compared to patients with normal blood flow.

Study Design

This is a multicenter prospective observational study.

Study Population

Patients with symptomatic vertebrobasilar stenosis (\geq 50%) or occlusion.

Study Evaluations

Noninvasive magnetic resonance (MR) imaging consisting of quantitative magnetic resonance angiography (QMRA) and MR perfusion imaging to assess intracranial blood flow.

Number of Participants

80

Number of Clinical Sites

6

Primary Endpoint

• Fatal and nonfatal ischemic stroke in the vertebrobasilar territory within 12 months.

1/21/15 Footnote: the definition used by the adjudication committee per [name] is, "Ischemic stroke is defined as new neurological symptoms or signs lasting at least 24 hours or lasting less than 24 hours but associated with new infarct on CT or MRI".

Secondary Endpoints

- TIA and fatal and nonfatal ischemic stroke in the vertebrobasilar territory.
- Ischemic stroke in any vascular territory.
- All ischemic stroke and vascular death.
- Aggregate of any ischemic stroke, myocardial infarction and vascular death.
- All stroke (ischemic and hemorrhagic).
- All death (vascular and nonvascular).
- Neurological impairment by NIH Stroke Scale (NIHSS).
- Neurological disability by modified Barthel Index (BI).
- Handicap by modified Rankin Scale (MRS) and modified Glasgow Outcome Score (GOS).

Principal Investigator

[name], FACS Assistant Professor of Neurosurgery University of Illinois at Chicago

Data Management

[name]

Data Management Center, Stroke Center University of Illinois at Chicago

1.2 OBJECTIVES

Primary Objective:

• To test the hypothesis that among patients with symptomatic vertebrobasilar disease (VBD), those with distal blood flow compromise are at higher risk of subsequent posterior circulation stroke than those with normal flow.

Secondary Objectives:

- To determine the correlation between large vessel flow (QMRA) and tissue level perfusion (MR perfusion) in the posterior circulation, and the predictive value of each modality.
- To determine other predictive factors for stroke in this population.
- To determine the hemodynamic effects of varying degrees of vertebrobasilar stenosis and occlusion.
- To determine changes in hemodynamic status of patients on medical therapy over time.
- To determine the utility of QMRA as a non-invasive screening and monitoring tool in symptomatic vertebrobasilar disease (VBD).

1.3 BACKGROUND AND RATIONALE

Approximately 700,000 strokes occur annually in the U.S. making it the third leading cause of death and the leading cause of permanent disability among adults. Posterior circulation strokes account for 30-40% of all ischemic strokes, resulting in approximately 200,000 cases per year. Atherosclerotic disease of the vertebrobasilar system is an important etiology of posterior circulation stroke¹. **Symptomatic vertebrobasilar disease (VBD)** carries a high annual risk of stroke, averaging 10-15% per year despite medical therapy. Vertebrobasilar stroke is particularly prone to resulting in devastating consequences due to the concentrated 'eloquence' of brain tissue supplied by the posterior circulation ². Consequently, vertebrobasilar stroke can result in high rates of death and disability.

Risks of stroke in VBD

Several retrospective studies have estimated the risk associated with vertebrobasilar stenosis (50-99%) to be **10-15% per year** ³⁻⁵. These stroke rates approach those seen with symptomatic high grade extracranial carotid stenosis. In a retrospective study of 44 patients with distal vertebral artery (VA) or basilar artery (BA) stenosis of \geq 50%, Mouffarij et al. reported a 27% incidence of vertebrobasilar ischemic events, with 5 of 12 events being stroke rather than TIA³. An overall 80% stroke free survival at 2 years was evident in this study. A study by Qureshi et al. of 102 patients with symptomatic VBD (>50% stenosis) demonstrated that 14% of patients experienced recurrent stroke, with a stroke free survival of only 72% at two years⁵. Retrospective analysis from the WASID study group⁶ examined the risk of stroke in 68 patients with symptomatic intracranial vertebrobasilar 50-99% stenosis treated with aspirin or warfarin over a median follow-up of 13.8 months. Fifteen (22%) of the patients suffered stroke, of which four (27%) were fatal. They reported an overall stroke risk of 13.6 to 15 per 100 patient years for stroke in the territory of the stenotic artery⁴. Data from the prospective WASID trial comparing use of warfarin versus aspirin in symptomatic intracranial stenosis of 50-99% in 569 patients demonstrated that 15% of patients suffered stroke in the territory of the stenotic artery⁷. The

incidence of stroke at one year was 12%, with stroke rates that were not significantly different between the anterior and posterior circulation⁸. In another recent prospective study of patients with intracranial stenosis \geq 50%, ischemic events were reported for the 49 patients of the full cohort of 102 patients who harbored symptomatic vertebral or basilar disease. The frequency of recurrent ischemic events (TIA and stroke combined) was found to be 42.8% during a mean follow-up of 23.4 months⁹.

The predominant stroke mechanism for patients with VBD appears to be regional hypoperfusion¹⁰; although thrombotically active plaques are a prominent feature of symptomatic carotid disease, this mechanism appears less prominent as the primary cause of ischemia related to vertebrobasilar stenosis. The posterior circulation vascular anatomy can allow for potential compensations to maintain distal arterial territory flow through collaterals (such as the posterior communicating arteries) in the setting of proximal vessel stenosis or occlusion. The existence and extent of these compensatory blood flow pathways, therefore, may influence the risk of stroke.

Rationale for use of QMRA and MR Perfusion

Various imaging techniques exist for assessing cerebrovascular hemodynamic compromise, including SPECT, PET, Xenon CT and TCD. These modalities are generally aimed at assessing cerebral tissue perfusion, and have proven valuable in assessment of anterior circulation flow compromise. However, these modalities have been less useful in the posterior circulation due to factors such as inadequate spatial resolution for the compact brain territory involved, and bony skull base artifacts. An alternative strategy is therefore desirable. Measurement of large vessel flow in affected and major collateral vessels in the posterior circulation is one such strategy, and can be obtained non-invasively using phase contrast QMRA¹¹⁻¹⁴. QMRA imaging can be easily combined with MR perfusion imaging to provide both large vessel and tissue level hemodynamic assessment.

The technique of phase contrast QMRA allows volumetric flow to be measured directly and noninvasively in the craniocervical vasculature, and has been shown to be accurate in both the in vitro and in vivo setting¹⁵⁻¹⁹. Standardized QMRA software is available as NOVA (Noninvasive Optimal Vessel Analysis), and has been used extensively to assess patients with cerebrovascular disease at the central coordinating site, University of Illinois at Chicago (UIC). A retrospective non-blinded cohort study examining outcomes of patients with symptomatic VBD demonstrated a significantly higher risk of subsequent stroke in patients with hemodynamic impairment as assessed by NOVA QMRA. Furthermore, QMRA may provide an appropriate non-invasive screening and follow-up monitoring tool in patients with known or suspected VBD.

Unlike QMRA which provides information regarding volumetric flow within a given vessel, MR perfusion imaging provides characterization of tissue level perfusion in the brain territory of interest²⁰. MR perfusion imaging is readily available on most clinical scanners, and can provide information regarding tissue level hemodynamic compromise. Therefore, tissue perfusion measurements may provide important correlative and predictive data for the conductance flow data from the large vessels obtained using phase contrast QMRA.

Rationale for the VERiTAS study

VBD represents a potentially treatable high risk source of stroke. Advances in endovascular angioplasty and stenting have created new options for the treatment of VBD, but the interventions themselves carry significant risks^{21, 22}, and the selection criteria for appropriate candidates remains uncertain. Our preliminary published retrospective data²³ suggests that the

risk of stroke in VBD is affected by the extent to which intracranial blood flow is compromised. Specifically, our analysis has indicated that patients with low intracranial flow as assessed by noninvasive QMRA are at significantly higher risk of stroke than those with normal flow. The objective is now to conduct a prospective longitudinal study of patients with symptomatic VBD to determine if level of blood flow compromise assessed by QMRA and MR perfusion at the baseline examination predicts risk of recurrent ischemic events.

[figure not shown]
1.4 STUDY DESIGN

The study is a multi-center prospective cohort study. Eligible patients will undergo, in addition to standard assessments, a QMRA imaging study and MR perfusion study to assess their cerebrovascular hemodynamic status, the results of which will be interpreted centrally and kept blinded from the clinicians caring for the patient.

The patients will be prospectively followed for a minimum of one year, and a maximum of two years, on current standard medical regimen to include standard stroke/cardiovascular risk factor modification and medical therapy, and evaluated for recurrent ischemic events.

We anticipate enrollment of a minimum of four patients per year per site over four years with a minimum of one-year of follow-up.

1.5 STUDY SCHEMA

1.6 ELIGIBILITY CRITERIA

Inclusion Criteria:

- Symptomatic patients (TIA or stroke) in the vertebrobasilar territory.
- Conventional angiography or CT angiography (CTA) demonstration of ≥ 50% stenosis or occlusion of extracranial or intracranial vertebrobasilar artery.
 - jpeg sent to CCC for confirmation prior to enrollment.
- Symptoms within 60 days of enrollment.
- Age 18 and above.
- Able to provide informed consent.

Exclusion Criteria:

1. Neurologic criteria:

- Major disabling stroke prohibiting the ability to return for follow-up assessment.
- Any neurological disease which would confound follow-up assessment.
- 2. Medical criteria:
 - Any severe co-morbidity condition with less than 12 month life expectancy.
 - Known cardiac disease associated with cardioembolic risk specifically atrial fibrillation, prosthetic valves, endocarditis, left atrial/ventricular thrombus, cardiomyopathy with EF<25%, cardiac myxoma.
 - Blood dyscrasias, specifically polycythemia vera, essential thrombocytosis, sickle cell disease.
- 3. Disease criteria:
 - Non-atherosclerotic disease vertebrobasilar disease including dissection, fibromuscular dysplasia, vasculitis, radiation induced vasculopathy.
 - Unilateral vertebral stenosis or occlusion
- 4. Patient criteria:
 - Unable or unwilling to undergo MRI.
 - Unable to undergo conventional angiography or CT angiography (CTA).
 - Pregnancy.
 - Concurrent participation in an interventional trial for treatment of vertebrobasilar disease.

Renal dysfunction will be exclusionary if it precludes angiography. Renal dysfunction will not be exclusionary if it precludes gadolinium administration as such patients may be enrolled but will not undergo the MR perfusion portion of the study imaging protocol, and thus, will not receive gadolinium. No subjects will be excluded based upon gender, race, ethnic group, religion or socioeconomic status. Children will not be recruited, as atherosclerotic VBD is a condition that affects adults primarily in later life and is not a disease that occurs or is relevant in children.

1.7 PATIENT RECRUITMENT AND ENROLLMENT

Patients presenting with vertebrobasilar distribution TIA or stroke are the source group of patients. Diagnostic evaluation of these patients will be performed at the discretion of the treating physicians at the participating center, but commonly includes one or more of several imaging modalities: magnetic resonance angiography (MRA), computed tomographic angiography (CTA), transcranial Doppler (TCD), or conventional angiography. Those patients who demonstrate evidence of \geq 50% vertebrobasilar stenosis by any of these diagnostic

imaging are potentially eligible for the study, and will be reported to the study site coordinator or any key research personnel who will assist in consenting. Patients will be identified through the Neurosurgery, Neuroendovascular and Neurology services at the participating centers. No study procedures will take place prior to subject consenting.

At sites where conventional angiography or CTA is not standard of care, subjects will be asked to undergo the informed consent process and sign the consent form prior to determination of final eligibility (the consent form will include consent for angiography to determine final eligibility). Subjects who meet angiographic inclusion criteria will continue with the study procedures; subjects who do not meet angiographic criteria will be withdrawn from the study. This will be outlined in the consent form. At sites where conventional angiography or CTA is routine, subjects will be consented based on presence of inclusive angiographic criteria. Patients with angiographically confirmed \geq 50% vertebrobasilar stenosis who meet the clinical entry criteria and sign the consent form will be enrolled.

Enrollment

Eligible patients who agree to participate in the study will sign written informed consent documents, and will be considered enrolled into the study. As part of the process of informed consent the patient will be told the purpose of the study, and that the study entails undergoing MR scans, and clinical follow-up to assess for occurrence of stroke and TIA. Consent will be documented by signing a consent form approved by the participating site Institutional Review Board (IRB). At the time of the enrollment, patients will fall into two categories:

1. Patients who have undergone or are scheduled to undergo conventional catheter angiography or CTA performed as part of standard work-up.

2. Patients for whom conventional catheter angiography or CTA is not considered to be part of the standard work-up: the participant is informed of the protocol requirement for catheter angiography or CTA at the time of informed consent, and single or bilateral vertebral vessel injection conventional angiography, or head and neck CTA, will be performed as part of the study. Any patients not meeting the angiographic criteria of \geq 50% vertebrobasilar stenosis will not continue as participants in the study and will not undergo the study procedures described below.

1.8 STUDY PROCEDURES

Baseline Evaluations

Clinical Evaluation:

Following enrollment and confirmation of angiographic stenosis \geq 50%, baseline assessments by the participating study coordinator and study physician are performed. This will consist of a thorough clinical and neurological evaluation including review of recent hospital records, and imaging studies. Clinical information including the nature and frequency of cerebral ischemic events will be gathered. Medications at the time of enrollment will be recorded. Data regarding standard stroke risk factors will be specifically recorded including the following baseline history: age, gender, race, hypertension, diabetes mellitus, lipid disorder, coronary disease, smoking, alcohol consumption, and parental death from stroke. A neurological evaluation will be performed. The NIHSS will be recorded and functional status will be measured using the Barthel Index, modified Rankin Scales and modified Glasgow Outcome Score. The data will be recorded on web-based standardized case report forms.

MR imaging:

An MR imaging protocol consisting of QMRA and MR perfusion will be performed at time of enrollment. The study is performed based upon a pre-specified protocol utilizing standardized

NOVA software. The NOVA portions of the study will be transferred via secure internet based transfer to the clinical coordinating site at UIC for central review by a certified NOVA interpreter. The MR perfusion portion of the study will be sent via sFTP transfer or CD to the clinical coordinating center at UIC for central review by a specified neuroradiologist. The results of the study will remain blinded to the patient and participating site personnel including the evaluating study physician.

The imaging protocol will be performed with the use of NOVA software installed on Siemens, G.E. or Phillips 3.0 Tesla MR scanners. The protocol will involve an approximately 60 minute MR scan consisting of initial time of flight (TOF) imaging of the cranial and cervical vasculature to include 15 vessels. A 3-D image of the vessels will be created, based upon which sites for blood flow measurement will be marked. Phase contrast MRA imaging will then be performed in the plane perpendicular to the identified sites to obtain blood flow measurement at those sites. MR perfusion will be performed using the dynamic susceptibility contrast (DSC) technique.

Standard management

Risk factor modifications

Patients will be placed on a standard medical regimen to include antithrombotic agents and standard stroke/cardiovascular risk factor medical therapy as managed by the participating center study physician in conjunction with the patient's primary care physician.

Follow-up evaluations

Monthly telephone follow-up assessment

The participating site study coordinator will contact patients monthly by telephone until 12 months for determination of new events. If a potential endpoint is identified treating physician will be notified, and the participating site arranges for the patient to be evaluated by the blinded study physician within 72 hours. If a stroke is clinically suspected, brain imaging with CT or MR will be performed in accordance with standard clinical management. The data from the telephone interviews will be recorded using standardized web-based case report forms.

Clinical visit follow-up assessment

In person follow-up will be performed at the participating site at 6 months (m), and 12m as a minimum, and every 6m thereafter up until completion of the study or 2 years maximum. A detailed neurological evaluation and assessment for new symptoms or signs will be performed at these visits. Interval occurrence of any symptoms of cerebrovascular disease or other medical problems will be determined. Clinical evaluations will be performed by the blinded study physician unfamiliar with the results of the study MR imaging. The patient's medication regimen and NIHSS Score will be recorded. The data will be recorded using standardized web based data forms.

MR imaging follow-up assessment

The MR imaging protocol will be repeated at 6m and 12m, at a minimum, and at 24 months if prior to the completion of the study. Results will be centrally reviewed and the results will remain blinded from the participating center.

Time course of assessments and follow-ups

| MONTHS | 0 | 1* | 2* | 3* | 4* | 5* | 6* | 7* | 8* | 9* | 10* | 11* | 12* | 18 | 24 |
|---------------------|---|----|----|----|----|----|----|----|----|----|-----|-----|-----|----|----|
| Demographics | х | | | | | | | | | | | | | | |
| Baseline Evaluation | х | | | | | | | | | | | | | | |
| Angiogram/CTA | х | | | | | | | | | | | | | | |
| MR imaging | х | | | | | | х | | | | | | Х | | Х |
| Telephone interview | | х | х | Х | х | х | х | х | х | х | Х | Х | Х | | |
| Clinical Follow-up | х | | | | | | х | | | | | | Х | х | Х |
| Evaluation | | | | | | | | | | | | | | | |
| NIHSS, BI, MRS, GOS | Х | | | | | | Х | | | | | | Х | Х | х |

*Minimum follow-up for all recruited patients (12m). Maximum is 24m.

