1.9 STUDY ENDPOINTS

Primary endpoint:

• Stroke (fatal and nonfatal ischemic stroke) in the vertebrobasilar territory at 12 months.

Secondary endpoints:

- TIA and fatal and nonfatal ischemic stroke in the vertebrobasilar territory.
- Ischemic stroke in any vascular territory.
- All ischemic stroke and vascular death.
- The aggregate of ischemic stroke, myocardial infarction and vascular death.
- All stroke (ischemic and hemorrhagic).
- All death (vascular and nonvascular).
- Neurological impairment as determined by the NIH Stroke Scale.
- Neurological disability as determined by the modified Barthel Index.
- Handicap as determined by the modified Rankin Scale and Glasgow Outcome Score.

Ischemic stroke is defined as new neurological symptoms or signs lasting at least 24 hours or lasting less than 24 hours but associated with new infarct on CT or MRI. TIA is defined as new neurological symptoms or signs lasting less than 24 hours without radiographic correlate of infarct. Vascular death is defined as a death of known vascular etiology or sudden death that could not be explained by a known nonvascular process.

Initial determination of endpoints will be defined by the participating site study physician but will be ultimately be independently determined by a central adjudication committee.

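### The impairment, disability and handicap scales are scheduled only at on-site visits, with no route to a score for a living patient whose stroke during follow-up prevents return

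*Protocol*

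**What the plan says.** All in the Protocol:

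- **Endpoints (1.9).** The scales are secondary endpoints, for example "Neurological impairment as determined by the NIH Stroke Scale" and "Neurological disability as determined by the modified Barthel Index"; the modified Rankin Scale and Glasgow Outcome Score measure handicap.
- **Visits (1.8, Clinical visit follow-up assessment).** "In person follow-up will be performed at the participating site at 6 months (m), and 12m as a minimum", then every six months to a maximum of two years. On what is recorded there, the text says "The patient's medication regimen and NIHSS Score will be recorded" and names no other scale.
- **Time-course table (1.8).** The row "NIHSS, BI, MRS, GOS" is marked at months 0, 6, 12, 18 and 24, the same months as the clinical follow-up row.
- **Telephone calls (1.8).** "The participating site study coordinator will contact patients monthly by telephone until 12 months for determination of new events". No scale is mentioned.
- **After a possible event (1.8).** "the participating site arranges for the patient to be evaluated by the blinded study physician within 72 hours". Again no scale is mentioned.
- **Entry (1.6).** One exclusion is "Major disabling stroke prohibiting the ability to return for follow-up assessment". No matching provision covers a patient who reaches that state after enrolment.

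**The concern.** The exclusion criterion shows that the authors knew a severe stroke can stop a patient from coming back. The primary endpoint event can put an enrolled patient in exactly that position, and section 1.3 stresses how often vertebrobasilar stroke disables. If the scales are taken only at the site, the worst-off survivors are the ones without a score, so the outcome itself causes the value to be missing. Under the study hypothesis these patients are mostly in the low-flow group. A comparison of disability or handicap by flow status would then understate the difference.

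This is a matter of data collection rather than analysis. An SAP can say how to handle a missing score, but it cannot recover a Rankin or Barthel score that nobody obtained from a living patient.

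**Working it through.** The protocol gives no figure for this point, so there is none to reproduce. The calculation below is an illustration.

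**Inputs from the Protocol**
- Annual event rates 0.22 (low flow) and 0.02 (normal flow), and 10% attrition from 80 patients (1.10): 80 × 0.9 = 72 evaluable.
- Stroke fatality 4/15, from a retrospective series cited in 1.3.

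**Assumptions (not in the Protocol)**
- Equal groups, 36 and 36.
- 10% to 30% of stroke survivors cannot return.
- Barthel Index 95 without stroke, 85 after stroke if able to return, 20 if unable to return, 0 if dead. The zero for death is a device for this illustration only.

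**Step 1: living patients without a score**

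n × event rate × (1 − 4/15) × share unable to return

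| | Low flow | Normal flow |
|---|---|---|
| Strokes | 36 × 0.22 = 7.92 | 36 × 0.02 = 0.72 |
| Fatal (× 4/15) | 2.11 | 0.19 |
| Survivors | 5.81 | 0.53 |
| Unable to return, 10% | 0.58 | 0.05 |
| Unable to return, 30% | 1.74 | 0.16 |

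The loss is 11 times as frequent in low flow (0.22/0.02).

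**Step 2: mean Barthel Index with every patient scored**

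- 10%, low flow: (28.08 × 95 + 5.23 × 85 + 0.58 × 20 + 2.11 × 0)/36 = 86.8. Normal flow: 94.3. Difference 7.5.
- 30%, low flow: (28.08 × 95 + 4.07 × 85 + 1.74 × 20 + 2.11 × 0)/36 = 84.7. Normal flow: 94.1. Difference 9.4.

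**Step 3: the same with deaths still scored and only the living non-attenders missing**

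- 10%, low flow: (28.08 × 95 + 5.23 × 85)/(36 − 0.58) = 87.9. Normal flow: 94.4. Difference 6.5. Attenuation 1 − 6.50/7.49 = 13%.
- 30%, low flow: (28.08 × 95 + 4.07 × 85)/(36 − 1.74) = 88.0. Normal flow: 94.4. Difference 6.4. Attenuation 1 − 6.43/9.39 = 32%.

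In points, the shortfall is about 1.0 to 3.0.

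**Step 4: sensitivity**

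- *Comparison confined to survivors.* The full difference is 2.6 (10%) to 4.6 (30%) and the observed one 1.4 to 1.2: a shortfall of about 1.1 to 3.5 points, or 44% to 75% of a smaller difference. The percentage depends heavily on how deaths enter; the shortfall in points does not.
- *Smaller low-flow share.* At 30% low flow (21.6 of 72) the living patients without a score number 0.35 to 1.05 in low flow and 0.07 to 0.22 in normal flow. The expected group means do not change, because they depend on proportions and not on group size.

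**The case against.** **The table does not tie the scales to the visit.** The scales have their own row, and months 6 and 12 also carry a call, so on-site scoring is an inference. It is a strong one: the scale row matches the clinical row in every column, including months 18 and 24 where no call is scheduled, and the calls have a stated purpose that does not include scoring. The visit text also does not say that NIHSS is the only scale taken; the table supplies the rest. That mismatch calls for tidying and is not a separate error.

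**There is another contact.** The evaluation within 72 hours of a possible event might yield a score. No scale is named there, and an acute score would not stand in for the 6- or 12-month outcome.

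**The consequence is limited.** This stands. The scales are the last-listed secondary endpoints, no objective in 1.2 concerns disability, and 1.10 specifies no flow-group contrast on them. The expected loss is one or two patients.

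**A reader might infer that patients who die have no score.** The Protocol does not say so. A death can be scored without a visit, the rule is commonly set in the SAP, which is not at hand, and death is a separate endpoint. The same holds for whether the scales are analysed as ordinal.

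**A reader might also infer that the low-flow group would look falsely well.** The figures do not support this. In every Barthel scenario above low flow stays worse. Attenuation of 81% to 88% appears only if deaths are also dropped from the observed comparison (1.4 against 7.5, or 1.2 against 9.4), which the Protocol does not specify. A separate illustration using the proportion with poor outcome reverses sign, slightly, only when deaths and all disabled survivors are removed.

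**Conclusion.** The point holds for living patients. Section 1.8 gives no way to score a survivor too disabled to attend, and the loss depends on the outcome and falls mainly in the low-flow group.

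The size is modest: about 0.6–1.7 low-flow patients against 0.05–0.16 normal-flow patients, and roughly 13–32% attenuation of the Barthel difference when deaths are scored. The event rates are the Protocol's. The fatality comes from 15 strokes in one cited series. The equal split, the share unable to return and the Barthel values are assumptions, so the direction is firmer than the percentage.

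The primary endpoint and the stroke and death endpoints do not need a scale score: monthly calls to month 12 and central adjudication serve them without one. The change is worth making because it is cheap and must be made before the data are collected.

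**What to change.** In section 1.8:

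1. State that when a patient cannot attend, the modified Rankin Scale, Barthel Index and Glasgow Outcome Score are obtained from the patient or a caregiver at the month-6 and month-12 calls already scheduled.
2. For months 18 and 24, where no call is planned, provide one call or a review of records.
3. Make the visit text list all four scales, as the table does.

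The cost is a few minutes on existing calls and an occasional extra contact, for a handful of patients; sample size and visits do not change. Telephone or caregiver scores are somewhat less precise than examined ones, so the mode of assessment should be recorded. NIHSS needs an examination and will stay missing for living non-attenders. The scoring of deaths and the form of analysis can be left to the SAP.
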